2.3.1.3 Medical history and current medical condition

Relevant medical history and current medical conditions (other than psoriasis, psoriatic arthritis, and cardiovascular diseases) present prior to signing of the informed consent and until the start of study treatment i.e. secukinumab, will be presented by primary system organ class (SOC) and preferred term (PT). coded using the Medical Dictionary for Regulatory Activities terminology (MedDRA version 20.1 or higher).

Medical Histories/conditions will be summarized for the FAS set (displaying totals) coded using the Medical Dictionary for Regulatory Activities (MedDRA) terminology version 22.1 or higher. The primary SOC's will be presented in alphabetical order. Preferred terms will be sorted by decreasing proportion and alphabetical order.

The tuberculosis (TB) assessment result (active TB, latent TB and no TB) will be summarized (displaying totals) as part of medical history. TB assessment details as collected on the TB assessment CRF will be listed separately for the FAS set.

2.4 Treatments (study treatment, rescue medication, concomitant therapies, compliance)

2.4.1 Study treatment

The number and percentage (%) of patients receiving injections will be summarized categorically (one less than all, two less than all etc.) for the core study using the SAF set by

treatment groups and overall. The duration of exposure (days) to secukinumab study treatment will be presented similarly.

[Duration of exposure is calculated as (last known date of study medication (as per the DAR CRF) – start date of medication) + 1] / 7 (in weeks)

The duration of exposure will be reported in weeks.

Start date and last known date of study medication will be as per the drug accountability record eCRF page.

2.4.2 Study compliance

2.4.2.1 Secukinumab

Compliance as percentage of injections administered will be calculated as the number of injections applied (based on documented study drug administrations and syringe counts as given in the dosage administration record eCRF page) divided by the number of injections scheduled per protocol. It is to be noted that for dropouts/discontinuations, the denominator will be adjusted to number of injections scheduled per protocol until discontinuation.

It is given by the formula:

Compliance (%) = $100 * (\text{total no of injections administered}) / (\text{no. of injections prescribed until discontinuation})$

In the core study selection phase Secukinumab 300 mg, two autoinjectors containing 150 mg Secukinumab, will be provided as open label medication at weeks 0, 1, 2, 3, 4, 8, 12, 16, 20 and 24 (last injection is at week 24).

Compliance percentage will be summarized for the SAF dataset (displaying totals) by treatment group and also by categories (< 80% and ≥ 80% to 100%).

2.4.2.2 Lifestyle intervention

Compliance as percentage of lifestyle intervention visits participated in will be calculated as the number of intervention visits attended (based on documented participation counts as given in the lifestyle intervention record eCRF page) divided by the number of lifestyle intervention visits scheduled per protocol until discontinuation. It is to be noted that for dropouts/discontinuations, the denominator will be adjusted to number of intervention visits participated scheduled per protocol until discontinuation.

It is given by the formula:

Compliance (%) = $100 * (\text{total no of lifestyle intervention visits participated}) / (\text{no. of lifestyle intervention visits scheduled})$

In the core study selection phase lifestyle intervention visit are scheduled at weeks 0, 1, 2, 3, 4, 8, 16 and 24. In the extension study phase the visits are scheduled for weeks 36, 44 and 56. Patients in Arm A starting lifestyle intervention during the extension phase will have their first

lifestyle intervention at week 28. Patients in Arm A do not have a lifestyle intervention at week 56. Patients in Arm B have lifestyle intervention visits at E1, E2 and E3.

Compliance percentage will be summarized for the SAF dataset (displaying totals) by treatment group and also by categories (< 80% and ≥ 80% to 100%).

2.4.3 Prior, concomitant and post therapies

Prior and concomitant medications along with non-drug therapies will be summarized using the SAF set by treatment group, separately.

Prior medications are defined as treatments taken and stopped prior to first dose of secukinumab study treatment. Any medication given at least once between the day of first dose of secukinumab study treatment and the last day of study visit will be a concomitant medication, including those which were started pre-baseline and continued into the treatment period.

Medications will be presented in order of frequency, by Anatomical Therapeutic Classification (ATC) codes and grouped by anatomical main group. Preferred terms will be sorted by decreasing proportion and alphabetical order.

Tables will also show the overall number and percentage of subjects receiving at least one treatment in a particular ATC code.

2.5 Analysis of the primary objective

2.5.1 Primary endpoint

The primary variable is the percentage of patients achieving PASI90 at week 28 in both randomized treatment arms, Secukinumab alone and Secukinumab combined with lifestyle intervention.

The primary analysis will be to demonstrate that the combination of Secukinumab (300 mg, 4-weekly s.c.) with lifestyle intervention results in higher psoriasis treatment efficacy than Secukinumab alone with respect to the primary endpoint in the FAS.

PASI score will be derived as indicated in Table 2-1. The head, trunk, upper limbs and lower limbs are assessed separately for erythema, thickening (plaque elevation, induration), and scaling (desquamation). The average degree of severity of each sign in each of the four body regions is assigned a score of 0-4. The area covered by lesions on each body region is estimated as a percentage of the total area of that particular body region. Further practical details to help with the assessment are provided below:

1. The neck is assessed as part of the head
2. The axillae and groin are assessed as part of the trunk
3. The buttocks are assessed as part of the lower limbs
4. When scoring the severity of erythema, scales should not be removed

Because the head and neck, upper limbs, trunk and lower limbs correspond to approximately 10%, 20%, 30% and 40% of the body surface area, respectively, the PASI score is calculated using the formula:

$$\text{PASI} = 0.1(\text{E}_\text{H} + \text{I}_\text{H} + \text{D}_\text{H})\text{A}_\text{H} + 0.2(\text{E}_\text{U} + \text{I}_\text{U} + \text{D}_\text{U})\text{A}_\text{U} + 0.3(\text{E}_\text{T} + \text{I}_\text{T} + \text{D}_\text{T})\text{A}_\text{T} + 0.4(\text{E}_\text{L} + \text{I}_\text{L} + \text{D}_\text{L})\text{A}_\text{L}$$

The keys for the letters are provided in Table 2-1.

PASI scores can range from a lower value of 0, corresponding to no signs of psoriasis, up to a theoretic maximum of 72.0.

The baseline value for analysis of the PASI is collected at the Randomization Visit.

Table 2-1 The PASI scoring system

Body Region	Erythema (E)	Thickening (plaque elevation, induration, I)	Scaling (desquamation, D)	Area score (based on true area %, A)*
Head(H) †	0=none	0=none	0=none	0=no involvement
	1=slight	1=slight	1=slight	1=>0-<10%
	2=moderate	2=moderate	2=moderate	2=>10-<30%
	3=severe	3=severe	3=severe	3=>30-<50%
	4=very severe	4=very severe	4=very severe	4=>50-<70%
				5=>70-<90%
				6=>90-100%
Trunk(T) ‡	0=none	0=none	0=none	0=no involvement
	1=slight	1=slight	1=slight	1=>0-<10%
	2=moderate	2=moderate	2=moderate	2=>10-<30%
	3=severe	3=severe	3=severe	3=>30-<50%
	4=very severe	4=very severe	4=very severe	4=>50-<70%
				5=>70-<90%
				6=>90-100%
Upper limbs (U)	0=none	0=none	0=none	0=no involvement
	1=slight	1=slight	1=slight	1=>0-<10%
	2=moderate	2=moderate	2=moderate	2=>10-<30%
	3=severe	3=severe	3=severe	3=>30-<50%
	4=very severe	4=very severe	4=very severe	4=>50-<70%
				5=>70-<90%
				6=>90-100%
Lower limbs (L) §	0=none	0=none	0=none	0=no involvement
	1=slight	1=slight	1=slight	1=>0-<10%
	2=moderate	2=moderate	2=moderate	2=>10-<30%
	3=severe	3=severe	3=severe	3=>30-<50%
	4=very severe	4=very severe	4=very severe	4=>50-<70%
				5=>70-<90%

Body Region	Erythema (E)	Thickening (plaque elevation, induration, I)	Scaling (desquamation, D)	Area score (based on true area %, A)*
				6=>90-100%

*Percentage (not score) of body region (not whole body) affected will be entered in the eCRF †Neck is assessed as part of the Head (H) body region

‡Axillae and groin are assessed as part of the Trunk (T) body region

§Buttocks are assessed as part of the Lower limbs (L) body region

Definitions of efficacy variables based on PASI

The following definitions will be used in this study:

- **PASI 50 response:** subjects achieving $\geq 50\%$ improvement (reduction) in PASI score compared to baseline are defined as PASI 50 responders
- **PASI 75 response:** subjects achieving $\geq 75\%$ improvement (reduction) in PASI score compared to baseline are defined as PASI 75 responders
- **PASI 90 response:** subjects achieving $\geq 90\%$ improvement (reduction) in PASI score compared to baseline are defined as PASI 90 responders
- **PASI 100 response / remission:** complete clearing of psoriasis (PASI=0)

2.5.2 Statistical hypothesis, model, and method of analysis

The null hypothesis to be rejected is that the odds of response Week 28 are equal in both treatment groups. The corresponding alternative hypothesis is that the odds of response at Week 28 are higher under Secukinumab combined with lifestyle intervention compared to Secukinumab alone.

Let p_j denote the proportion of responders at Week 28 for treatment group j , $j=0, 1$, where

- 0 corresponds to Secukinumab combined with lifestyle intervention
- 1 corresponds to Secukinumab alone

The following hypotheses will be tested:

$$H_0: (p_1 / (1 - p_1)) / (p_0 / (1 - p_0)) = 1 \text{ versus } H_A: (p_1 / (1 - p_1)) / (p_0 / (1 - p_0)) \neq 1$$

In other words:

H_A : The odds ratio of achieving a response at Week 28 for Secukinumab combined with lifestyle intervention vs Secukinumab alone is different from 1.

The primary analysis will be performed on FAS dataset comparing treatments with respect to the primary efficacy variable in a logistic regression model with the factors treatment, center and covariate baseline PASI. The odds ratio and its 95% confidence interval (CI) and p-value will be given. The null hypothesis of equal odds will be rejected if the 2-sided p-value from the

logistic regression model for the factor “treatment” is < 0.05 ; however, superiority of Secukinumab combined with lifestyle intervention will be claimed only if the direction is correct, i.e. if the odds of response are larger under Secukinumab combined with lifestyle intervention.

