6.4.4 Weight and height

Height and body weight will be measured as listed in table 6-1, height in centimeters (cm) and body weight in kilogram (kg) (to the nearest 0,1 kg).

Height and body weight will be measured in indoor clothing, but without shoes. Whenever possible, body weight assessment should be performed by the same study site staff member; the same scale should be used throughout the study.

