2.8 Additional analysis

In order to explore the additional effect of lifestyle intervention on various related end-points an additional analysis will be performed for PASI 75, PASI 90 & PASI 100 and all the study biomarkers at V9 (Week 16), V12 (Week 28) and end-of-study i.e. Week 56 for both treatment arms, separately based on three below mentioned subgroups:

- Patients with weight loss <5%
- Patients with weight loss $\geq 5\%$ - < 10%
- Patients with weight loss $\geq 10\%$

For all the above mentioned sub-groups no. of patients falling in each sub-group will be descriptively summarized using frequency, percentages and exact 95% clopper-pearson CI at V9 (Week 16), V12 (Week 28) and end-of-study i.e. Week 56 for both treatment arms, separately using FAS. Change in weight loss will be compared from the baseline weight.

All the patients who achieved PASI 75, 90 & 100 at V9 (Week 16), V12 (Week 28) and end-of-study i.e. Week 56 will be descriptively summarized using frequency, percentages and exact 95% CI using clopper-pearson method for the above mentioned sub-groups in both treatment arms, separately using FAS. Further additional analysis will be performed on FAS dataset comparing treatments with respect to the PASI 75, 90 & 100 in a logistic regression model with the factors treatment, center and covariate baseline PASI. The odds ratio and its 95% confidence interval (CI) and p-value will be given. The above analysis will be performed for all the three sub-groups independently.

PASI score at baseline & PASI 75, 90 & 100 scores and biomarkers value will be descriptively summarized using N, n, Mean, median, standard deviation, min, max for all the three subgroups using FAS. All the summary statistics and analysis on biomarkers will be performed

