2.11 Interim analysis

A first analysis of the core study (primary, secondary [REDACTED] endpoints related to the core study) will be performed after all subjects have completed the core study.

[REDACTED]

The two analyses will be reported in separate clinical study reports.

3 Sample size calculation

This study is primarily designed to demonstrate superiority of secukinumab combined with lifestyle intervention vs Secukinumab alone in terms of PASI90 response at week 28. A PASI90 response of 81% at week 28 under Secukinumab alone in patients with metabolic syndrome is assumed. This number is based on a retrospective analysis performed with data from the CLEAR study, taking into account the slightly higher BMI of the patient population with metabolic syndrome (BMI 23-42 kg/m², Albareda M et al., 2014) and the open-label design.

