Evidence on effect size of lifestyle intervention on PASI response is relatively rare and assumptions were based on the following studies: A clinical study by [Al-Mutairi et al \(2014\)](#) showed an absolute increase of 27% in PASI75 response to biologic treatment (Infliximab, Etanercept, Ustekinumab, Adalimumab) in overweight or obese, moderate to severe psoriasis patients undergoing weight reduction compared to patients not undergoing weight reduction. However the dietary regimen used in this study was highly restrictive and consecutively led to a strong mean weight loss (-13 kg vs + 1,5 kg in the control group after 24 weeks). Naldi et al (2014) showed an absolute increase of 6% in PASI75 response to systemic treatment in overweight to obese, moderate to severe psoriasis patients undergoing diet and physical exercise compared to control patients. The lifestyle intervention in this study was less intensive and consecutively led to a smaller mean weight loss (-3kg vs -1.6 kg in the control group after 20 weeks). It seems that the extent of increase in PASI response correlates with the achieved weight loss, at least to a certain extent. PASI90 data were not available for both cited studies. The lifestyle intervention conducted in the present study is less intensive than the one applied by Al-Mutairi et al. but more intensive compared to Naldi et al. A lifestyle intervention very similar to the one applied in our study was previously able to show a mean weight loss of -3.8 kg vs. - 1.4 kg after 1 year (Kulzer B et al., 2014). Maximum weight loss can already be expected after 3-4 month. As part of the lifestyle intervention program activity tracking devices will be used in the present study to further support the lifestyle intervention.

Based on these considerations and the fact that we are looking at PASI90 response in the present study, we assume an absolute increase of 9% in PASI90 response in the Secukinumab combined with lifestyle intervention arm to 90% PASI90 responders compared to 81% PASI90 responders in the Secukinumab alone arm. An absolute increase of 9% in PASI90 responders would also be clinically meaningful.

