Based on these assumptions 342 patients per arm would provide a power of 90 % at a two-sided alpha of 0.05 to demonstrate that the percentage of PASI90 responders at week 28 is higher in the Secukinumab combined with lifestyle intervention arm compared to the Secukinumab alone arm. In case the true effect size would only be 7.5 %, this sample size would still provide a power of 75 %. To compensate for some expected drop out and/or premature discontinuations, 380 patients per arm are planned to be recruited for this study.

4 Change to protocol specified analyses

Below mentioned changes to the analysis described in Section 9 of the protocol version 02 are planned.

- i. Separate analyses will be performed for subjects with fasting and non-fasting status for fasting plasma glucose, fructosamine, and HbA1c in secondary analyses
- ii. Separate analyses will be performed for subjects with fasting and non-fasting status for all the biomarkers in biomarker sub-study
- iii. Additional analysis proposed for stratification of the analysis for PASI 75, PASI 90, PASI 100 and all study biomarkers by the groups “patients achieving weight loss < 5%”, “patients achieving weight loss $\geq 5\%$ - < 10%” and “patients achieving weight loss $\geq 10\%$ ” in each treatment arm.

5 Appendix

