5.2 Statistical models

5.2.1 Primary analysis

Logistic regression model

The proportions of patients who achieve a PASI 90 response at Week 28 for each treatment group will be compared using logistic regression analysis. The model will include treatment and center as fixed effect and with covariates PASI score at baseline (Visit 2).

The SAS procedure PROC GLIMMIX will be used with the following SAS code:

```
proc glimmix data=.... order=internal;  
class trtn1 cntr ;  
model response = trtn1 cntr basv2 / ddfm=kr error=binary  
link=logit;  
lsmeans trtn1 / cl diff oddsratio;  
run;
```

where

response = PASI 90 response (= 1 or 0)

trtn1 = treatment

cntr = center

basv2 = PASI score at baseline (Visit 2)

The estimated odds ratios will be displayed along with the associated 95% confidence intervals and p-values (two-sided).

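### The primary PASI90 model could take baseline body weight as a covariate at almost no cost; leaving it out is a missed improvement, not an error

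*SAP*

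**What the plan says.** Protocol 9.4.2 and SAP 2.5.2 give the same primary analysis, a "logistic regression model with the factors treatment, center and covariate baseline PASI". The code in SAP 5.2.1 agrees: "model response = trtn1 cntr basv2 / ddfm=kr error=binary", where the terms are treatment, center and Visit 2 PASI. The only sensitivity analysis (Protocol 9.4.4, SAP 2.5.4) is a Cochran-Mantel-Haenszel test stratified by center. Protocol 5.3 describes 1:1 randomisation and mentions no stratification by weight or BMI.

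The sample-size text (Protocol 9.8, SAP section 3) does bring BMI in. It states "A PASI90 response of 81% at week 28 under Secukinumab alone in patients with metabolic syndrome is assumed", a figure drawn from a retrospective analysis of an earlier secukinumab trial, "taking into account the slightly higher BMI of the patient population with metabolic syndrome" and the open-label design.

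The data are already planned. Protocol 6.4.4 says "Height and body weight will be measured as listed in table 6-1", and that table schedules height at Visit 1 and weight at every scheduled visit, including Visits 1 and 2. SAP 2.3.1.1 lists weight and BMI among the baseline characteristics. SAP 2.8 takes baseline weight as the reference for its weight-loss subgroups: "Change in weight loss will be compared from the baseline weight".

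**The concern.** The sample-size text treats BMI as relevant to the PASI90 rate, yet no analysis visible in the documents adjusts the primary endpoint for baseline weight or BMI. Randomisation is not described as balancing weight, so only chance does so.

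Two things are at stake, both small. A covariate that predicts response would buy some precision. And if the arms happen to differ in baseline weight, readers will ask how much of the result that difference explains. A covariate named in advance answers that; one added after the results are known is open to challenge. The weight-loss subgroups in SAP 2.8 cannot stand in for it, because they are formed after randomisation from a variable that the intervention is meant to change.

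**Working it through.** **Inputs from the documents.** Control rate 81%; "we assume an absolute increase of 9% in PASI90 response", hence 90%; "342 patients per arm would provide a power of 90 % at a two-sided alpha of 0.05"; 75% power at 7.5 points; 380 per arm recruited (SAP section 3). The prognostic strength of BMI is not given, so it is an assumption and is shown as a range.

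**Step 1. Reproduce the plan's sample size.** With p̄ = (0.81 + 0.90)/2 = 0.855:

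n₀ = [1.960·√(2·0.855·0.145) + 1.2816·√(0.81·0.19 + 0.90·0.10)]² / 0.09² = (0.976 + 0.633)² / 0.0081 ≈ 319.6, so 320 without a continuity correction.

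n = (n₀/4)·[1 + √(1 + 4/(n₀·0.09))]² = (319.6/4)·(2.0673)² ≈ 341.4, so **342**, an exact match. Continuity-corrected power at 342 per arm is 90.1% for 81% vs 90% and 74.7% for 81% vs 88.5%, which agrees with the stated 90% and 75%. 342/0.90 = 380. No stated figure is wrong.

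**Step 2. Power and type I error with and without the covariate.** Logistic regression was simulated with 342 per arm and 4,000 trials per setting. The marginal response rates were held at the planned values, and a standardised baseline covariate was left out or included. Power uses an uncorrected Wald test, which is why it lies near 92% rather than 90%.

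| Assumed OR per SD of BMI | 81 vs 90%: without → with | 81 vs 88.5%: without → with | Type I error: without → with |
|---|---|---|---|
| 1.0 | 92.7 → 92.7% | 77.7 → 77.8% | 4.6 → 4.5% |
| 0.8 | 91.5 → 91.6% | 77.6 → 78.0% | 4.8 → 4.9% |
| 0.67 | 92.0 → 92.4% | 77.6 → 78.8% | 4.6 → 5.0% |
| 0.5 | 92.1 → 93.4% | 78.4 → 81.0% | 5.0 → 5.2% |

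The gain is 0 to 1.3 points at the 9-point effect and 0.1 to 2.6 points at 7.5 points. Further runs at 81% vs 90% put the gain at an OR of 0.5 at 1.2 to 1.4 points, so about 0 to 1.5 is a fair summary for the design effect. The table omits center and baseline PASI. Smaller runs with about 100 fixed center effects also showed no loss.

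**Step 3. What the odds ratio then means.** At the 9-point effect the average estimated odds ratio is about 2.13 without the covariate and at most about 2.23 with it (at an OR of 0.5 per SD). The adjusted figure is conditional on the covariate, so the two are not the same quantity.

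**Step 4. Size of a chance imbalance.**
- SE of the between-arm difference in a standardised covariate at 380 per arm: √(2/380) = 0.0725 SD. Two SE = 0.145 SD.
- Design log odds ratio: ln(0.90/0.10) − ln(0.81/0.19) = 0.747 (OR 2.11).
- Shift at an assumed 0.3 log-odds per SD: 0.145·0.3 = 0.044, or 6% of 0.747. At 0.6: 0.145·0.6 = 0.087, or 12%.
- SE of the treatment log odds ratio at 380 per arm: √[1/(380·0.81·0.19) + 1/(380·0.90·0.10)] = 0.215. The shift is therefore 0.2 to 0.4 of one standard error.

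**The case against.** The strongest reply is that the planned model is valid as it stands. It is stated identically in the protocol, the SAP text and the code. Under randomisation, leaving out a further covariate neither biases the test nor raises the error rate. Ordinary chance imbalance is already covered by the confidence interval, and a two-SE imbalance arises in about one trial in twenty and favours either arm equally often. Baseline weight and BMI will be tabulated by arm, so an imbalance would be seen. All of this stands, and it is why this is an optional improvement.

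A reader might also infer more than the documents support:

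- *That BMI is shown to be a strong predictor of PASI90.* The sample-size text names BMI alongside the open-label design and gives no direction, size or coefficient. That it is prognostic is an inference.
- *That baseline weight confounds the comparison because the intervention works through weight.* The rationale (Protocol 1.1, 3.3 and 9.8) mainly concerns weight loss during the study and reduced systemic inflammation. An effect through weight change does not make baseline weight a confounder in a randomised trial.
- *That adjustment can never cost power.* No loss was seen in the settings simulated, but the full planned model, with baseline PASI as well as center, was not simulated.

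Parts of the exploratory section are redacted, so a weight-adjusted exploratory analysis there cannot be excluded. The primary and sensitivity analyses are fully visible.

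**Conclusion.** The point holds as a nearly free improvement. At the design effect the gain is about 0 to 1.5 points of power. At the low end of assumed prognostic strength it cannot be told from zero, and the upper end needs an odds ratio near 0.5 per SD, which the documents neither support nor rule out. At the smaller 7.5-point effect, where the plan itself expects only 75% power, the gain reaches 2.6 points under the same strong assumption. The other benefit is protection against an argument over chance imbalance worth 6 to 12% of the design effect in an unlucky trial. The conclusion rests on the assumed range of prognostic strength, and on body weight carrying similar information to the BMI named in the sample-size text.

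**What to change.** Add one continuous covariate, pre-dose baseline body weight, to the primary logistic model in Protocol 9.4.2, SAP 2.5.2 and the SAP 5.2.1 code, and to the PASI75/90/100 models that follow it (Protocol 9.5.1, SAP 2.6.1). Use the Visit 2 value, or Visit 1 if Visit 2 is missing, which is the baseline rule already in SAP 2.1.1.2. Name weight alone: leaving weight or BMI open would be a choice made late in a confirmatory model, and weight is measured at both visits whereas height is taken only at Visit 1.

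State that the odds ratio is conditional on baseline weight, center and baseline PASI. Do not adjust for on-treatment weight, which the intervention affects.

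The cost is one model term and a few words of text, with no new data and no change to the 342 or 380 per arm. The change counts as prespecified only if it is made before the core results are known; after that, the adjusted model should be presented as a supportive analysis.

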2.1.1 General definitions

Summary statistics for continuous variables will include N (the number of subjects in the analysis set), n (the number of subjects with available/imputed value), mean, standard deviation (SD), median, minimum & maximum. Summary statistics for discrete variables will be presented in contingency tables and will include absolute and relative frequencies for non-missing data. A row (category) denoted “Missing” will be included in count tabulations if a non-zero count of missing values is present. Percentages will be calculated using the number of patients in the relevant population or subgroup as the denominator. If a count of zero is obtained, the zero count and percentage will still be displayed.

If not otherwise specified, p-values will be presented as two-sided p-values along with the two sided confidence interval.

Unless otherwise stated, the level of significance will be set to 5% (two-sided).

Change from baseline and percentage change from baseline will only be summarized for subjects with both baseline and post-baseline values and will be calculated wherever applicable as:

Change from baseline = post-baseline value – baseline value.

Percentage change from baseline = ((Change from baseline value) / (baseline value)) * 100

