2.5.4 Sensitivity analyses

The primary endpoint will be analyzed by means of a Cochran-Mantel-Haenszel (CMH) test using the FAS set. This test will be stratified by center. Treatment groups will be compared with respect to the proportion of responders using the CMH test statistics. The corresponding p-values will be based on the CMH statistics which follows a Chi-square distribution with one degree of freedom.

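### No between-arm risk difference with a confidence interval is planned for the primary PASI90 endpoint; the only interval estimate of the effect is an odds ratio adjusted for about 100 small centres

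*SAP*

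**What the plan says.** The endpoint is defined on the percentage scale. SAP 2.5.1: "The primary variable is the percentage of patients achieving PASI90 at week 28 in both randomized treatment arms". The design assumptions use the same scale. SAP section 3 (and protocol 9.8): "A PASI90 response of 81% at week 28 under Secukinumab alone in patients with metabolic syndrome is assumed", rising to 90% with the lifestyle intervention, followed by "An absolute increase of 9% in PASI90 responders would also be clinically meaningful".

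The planned between-arm estimate is on the odds scale. SAP 2.5.2, repeating protocol 9.4.2: "The odds ratio and its 95% confidence interval (CI) and p-value will be given". The model has treatment and centre as factors and baseline PASI as covariate. In SAP 5.2.1 centre is a fixed effect and the output request is "lsmeans trtn1 / cl diff oddsratio". That returns logit-scale means, their difference and the odds ratio, with no back-transformation to proportions.

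The sensitivity analysis in SAP 2.5.4 is a CMH test stratified by centre: "The corresponding p-values will be based on the CMH statistics which follows a Chi-square distribution with one degree of freedom". No estimate is attached to it.

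The general rules in SAP 2.1.1 add: "Summary statistics for discrete variables will be presented in contingency tables and will include absolute and relative frequencies for non-missing data". SAP 2.5.3 counts a missing week-28 PASI as non-response, so every patient in the full analysis set has a response status.

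**The concern.** Assumed effect, sample size and the remark on clinical meaning are all in percentage points, yet the only interval around the treatment effect is for an odds ratio. When most patients respond, an odds ratio looks much larger than the change in the proportion responding, and its absolute meaning depends on the control rate. A reader of the main result would have two percentages and an odds ratio with its interval, but no planned statement of how precisely the extra proportion of PASI90 responders has been estimated.

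The odds ratio is also conditional on centre, and the centres are small. Protocol section 4 plans about 760 patients in about 100 sites, or 760/100 = 7.6 per site. One fixed parameter per small centre tends to push a maximum-likelihood odds ratio away from 1, so the one planned estimate may exaggerate the effect.

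**Working it through.** **Inputs.** Control 81%, lifestyle arm 90%, two-sided alpha 0.05, power 90%, 342 per arm, 380 per arm recruited (SAP section 3); 1:1 allocation (protocol 5.3); about 760 patients in about 100 sites (protocol section 4).

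**1. The plan's sample size.** With mean response 0.855:

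n = [1.96·√(2·0.855·0.145) + 1.2816·√(0.81·0.19 + 0.90·0.10)]² / 0.09² = 319.6, or 320.

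With continuity correction: (319.6/4)·[1 + √(1 + 4/(319.6·0.09))]² = 341.4, so 342 per arm. This matches. Continuity-corrected power at 342 per arm is 90.1% for 9 points and 74.7% for 7.5 points (81% vs 88.5%), matching the stated 90% and 75%. 342/0.90 = 380. So the stated sample size is that of a comparison of two proportions; a calculation on the log odds ratio would give 332.

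**2. The planned effect on each scale.** Odds ratio (0.90/0.10)/(0.81/0.19) = 2.11; risk ratio 0.90/0.81 = 1.11; difference 9 points.

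**3. What an odds ratio of 2.11 means at other control rates.** p1 = OR·p0/(1 − p0 + OR·p0). Rates other than 81% are assumptions to show the range.

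- 60%: 16.0 points
- 70%: 13.1 points
- 81%: 9.0 points
- 85%: 7.3 points
- 90%: 5.0 points

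**4. The interval the plan leaves out.** These are unadjusted calculations, so they approximate the planned model.

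- Observed exactly as planned, 380 per arm: SE = √(0.81·0.19/380 + 0.90·0.10/380) = 0.0253; 9.0 ± 1.96·2.53 gives about 4.0 to 14.0 points.
- Edge of significance, 380 per arm, pooled z test: 308/380 (81.1%) vs 328/380 (86.3%), difference 5.3 points, 95% CI 0.0 to 10.5, odds ratio 1.47. Wald log-odds and Fisher tests need 5.5 points (Wald odds ratio 1.51, 95% CI 1.02 to 2.23).
- Edge with 342 per arm: 5.6 points, 95% CI 0.0 to 11.1, odds ratio 1.51.

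**5. Effect of small centres on the odds ratio.** Simulated trials had 95 centres of 8 patients, 4 per arm, true rates 81% and 90% in every centre, centre fitted as a fixed effect, and no baseline-PASI term.

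- Median fixed-centre odds ratio about 2.33 to 2.36 across separate sets of runs, against a true 2.11: an excess of 2.33/2.11 = 1.10 to 2.36/2.11 = 1.12, so 10 to 12%.
- A smaller set of 150 trials gave 2.19 where the crude odds ratio in the same trials was 1.99, a ratio of 1.10.
- In that set 67.84 of the 95 centres on average had mixed outcomes. The other 27.16/95 = 29% had uniform outcomes and carry no information on this odds ratio.
- With an assumed centre SD of 0.5 on the logit scale, the median was 2.44 against a true conditional 2.16.
- The crude risk difference stayed at about 9.0 points.

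Converted back at an 81% control rate, 2.33 gives 2.33·0.81/(0.19 + 2.33·0.81) = 90.9% and 2.36 gives 91.0%. That is 9.9 to 10.0 points where the truth is 9.0.

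**The case against.** The strongest reply is that the absolute result is not hidden. The percentage per arm is itself the primary variable, the general rules require frequencies, and non-responder imputation leaves no missing status. The crude difference is one subtraction, and anyone can compute an unadjusted interval from the four counts. SAP 2.8 also plans responder percentages with exact intervals by arm at week 28, though only within weight-loss subgroups. All of this stands. A reader might infer that the result can be seen only as an odds ratio, or that the number of extra responders cannot be known; the documents do not support that. What remains is that no between-arm difference with an interval is specified, crude or centre-adjusted.

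A reader might also treat 9 points as the plan's own bar and a win near 5 points as a failure against it. SAP section 3 does not say this. The 9 points are a planning assumption that would also be clinically meaningful; they are not a minimum or a success criterion, and the same section reports power for 7.5 points. Winning below the planned effect is common to any design with 90% power: 1.96/(1.96 + 1.28) = 0.60, and 0.60·9 = 5.4 points. It does not come from choosing an odds ratio, and adding a risk difference would not change it.

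Finally, the hypotheses, model and code all use the odds scale, so the plan is consistent with itself. That also stands: this is a gap in estimation and reporting, with no error in the decision rule.

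**Conclusion.** The point holds as a modest one. For the primary endpoint the only planned between-arm interval estimate is an odds ratio conditional on centre and baseline PASI. The arm percentages will be visible, but the uncertainty of their difference is not planned for, so it cannot be set beside the 81% versus 90% on which the trial was sized. That uncertainty is material: about ±5 points at the planned effect with 380 per arm, and about 0.0 to 10.5 points at the edge of significance.

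The fixed-centre odds ratio is likely to run about 10 to 12% high in this design. That size rests on equal centres of 8, balanced arms and no baseline covariate; actual centre sizes would change it. The direction follows from fitting many fixed centre effects to few patients each.

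Nothing here shows that the primary test, its alpha or the sample size is wrong.

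**What to change.** Add to SAP 2.5.2 the number and proportion of PASI90 responders per arm at week 28 in the full analysis set. Add to SAP 2.5.4, beside the CMH p-value, the Mantel-Haenszel risk difference stratified by centre with its 95% CI, using a variance estimator suited to many small strata. Centres where every patient responds still contribute to this estimate. A centre with patients in only one arm gets no weight, so state in advance whether such centres are pooled.

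Optionally add the standardised difference in proportions from the primary logistic model. This takes more care: centres with uniform outcomes cause separation, so the handling of those centres and the variance method would have to be written down.

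Label these as supporting estimates. Describe the result next to the 9-point planning assumption, without making 9 points a relevance threshold. Hypothesis, test, alpha and sample size stay unchanged. The cost is a short SAP addition and a few lines of code on data already collected, somewhat more if the standardised version is included.
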